8.5 Clinical Laboratory Evaluation

Values at Screening and at 3 weeks post first dose, as described in Section 3, for laboratory parameters for hematology and clinical chemistry will be summarized by treatment group for the safety population using descriptive statistics. Values at Screening, Visit 3 (At Randomization), At First Dose, and at 3 Weeks Post First Dose, as described in Section 3, for laboratory parameters for urinalysis will be summarized by treatment group for the safety population using descriptive statistics.

Shift tables based on classification of values with respect to the reference range will be summarized for the safety population for critical clinical chemistry and hematology laboratory tests by treatment group. Critical clinical chemistry and hematology laboratory tests are listed in the appendix for Table Display Specifications.

Post-baseline elevations in alanine aminotransferase (≥ 3 times the upper limit of normal [ULN]), aspartate aminotransferase (≥ 3 times ULN), total bilirubin (≥ 1.5 times ULN) will be summarized by treatment group at Screening and at 3 Weeks Post First Dose.

Hematology, clinical chemistry, hepatic monitoring, urinalysis, and pregnancy results will be presented in data listings for subjects in the safety population.

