### **8.2.3 Visit 6: Stool Collection in Controlled Supervised Facility (Day 17 ± 7)**

Patients will be admitted for a maximum of 7 days to a facility providing supervised confinement for collection of stool for determination of CFA, CNA, and stool weight. The timing of the previous visits (Visit 1 and Visit 2) should be made with the aim of accommodating the patients' schedules for the supervised confinement. To accommodate patients' schedules for the supervised confinement, a ±7 day visit window is permitted.

- During the third week (Visit 3) (±1 week), patients will undergo admission to a controlled supervised facility for stool collection to support the CFA and CNA assessment and weight. A ±7 day visit window is allowed to accommodate investigative site staff and patients schedules for the supervised confinement.
- After appearance of fecal stool dye markers has been measured, patients CFA and CNA will be measured under their dose of MS1819-SD or prestudy dose of porcine PERT using standardized high-fat meals during the 3-day standardized diet.
- The CFA calculation will be based on the measured fecal fat content in relation to ingested fat quantities during the 3-day stool collection period.

After completion of the initial treatment period during the completion of V3, patients will be instructed to switch their study medication to either a fixed dose of MS1819-SD or their

---

prestudy porcine PERT. The stool collection and dietary procedures will be conducted as described in Section 8.3.3.1. (Instructions for Supervised Confinement)

The following procedures will be performed at Visit 6:

- Focused physical exam to evaluate gastrointestinal tract, heart, and lungs
- Record body height and weight
- Record vital signs while sitting (blood pressure, pulse rate, breathing rate, and temperature)
- Record any changes in AEs and concomitant medication
- Instruct/dispense study drug
- Verify study drug count on the last day of confinement
- Return MS1819-SD (only for patients randomized to MS-1819SD) on the last day of confinement
- Assess and record malabsorption signs and symptoms
- Begin 72-hour controlled diet
- Marker-to-marker stool collection and stool weight (central laboratory will weigh the stool that is collected)
- Collect urine sample for urinalysis
- Perform a urine pregnancy test (urine dip stick), if applicable
- Collect samples for hematology, clinical chemistry, PT/INR, and aPTT
- Collect samples for fasting lipids and prealbumin

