In order to present summaries by treatment group regardless of sequence, the following parameters will be summarized as described below: safety laboratory, vital signs, signs and symptoms of malabsorption, weight, BMI, and serum liposoluble vitamins A, D, E, and K. These endpoints will be summarized relative to the time of first dose on a given study treatment. All post-randomization measurements will be relative to the time of the first dose. For example, in the MS1819 treatment column, the measurement at first dose will be Visit 3 if a subject is randomized to the MS1819-PERT sequence, and Visit 6 if a subject is randomized to the PERT-MS1819 sequence.

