8.6 Vital Signs, Physical Findings, and Other Observations Related to Safety

8.6.1 Vital Signs

Values at Visit 3 (At Randomization), At First Dose, and at 3 Weeks Post First Dose, as described in Section 3, in systolic blood pressure, diastolic blood pressure, heart rate, respiratory rate, and temperature will be summarized by treatment group for the safety population using descriptive statistics.

Vital sign values will be presented in a data listing for all subjects in the safety population.

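### Chemistry, hematology and liver-elevation summaries lack the At First Dose reference (Visit 6 in Period 2) that SAP 3 defines, so a persistent Period 1 abnormality is shown under both treatments

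*SAP*

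**What the plan says.** SAP 3 sets the convention for presenting data by treatment regardless of sequence. It names the safety laboratory among the parameters covered and states: "These endpoints will be summarized relative to the time of first dose on a given study treatment". Its example is that, in the MS1819 column, "the measurement at first dose will be Visit 3 if a subject is randomized to the MS1819-PERT sequence, and Visit 6 if" the patient is in the PERT-MS1819 sequence.

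SAP 8.5 and 8.6.1 then list the time points to be shown:

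- Hematology and chemistry: "Values at Screening and at 3 weeks post first dose, as described in Section 3, for laboratory parameters for hematology and clinical chemistry".
- ALT, AST and total bilirubin elevations: these "will be summarized by treatment group at Screening and at 3 Weeks Post First Dose".
- Urinalysis: "Values at Screening, Visit 3 (At Randomization), At First Dose, and at 3 Weeks Post First Dose".
- Vital signs: "Values at Visit 3 (At Randomization), At First Dose, and at 3 Weeks Post First Dose".
- Shift tables: "Shift tables based on classification of values with respect to the reference range will be summarized for the safety population", for critical chemistry and hematology tests. The text names no baseline visit.

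Protocol 8.2.3 lists at Visit 6: "Collect samples for hematology, clinical chemistry, PT/INR, and aPTT". In the schedules (Protocol Table 1, SAP 13.2) these samples are taken at Visits 1, 6 and 9, and not at Visit 3. Crossover takes place at the end of the Visit 6 confinement (Protocol 8.2.3 and 8.3). There is no washout (Protocol 7.1, SAP 2.2).

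**The concern.** Safety is a primary objective, and SAP 8.1 says that summarizing by actual treatment allows a direct comparison of tolerability within each patient. For chemistry, hematology and liver tests, the only earlier value shown beside the 3-week value is Screening. For the treatment taken second, Screening precedes the whole of Period 1. The table therefore cannot tell an abnormality that began on the second treatment from one carried over from the first.

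The laboratory tables carry particular weight here. Protocol 9.1.1 keeps out of adverse event reporting those laboratory abnormalities that have no clinical manifestation, need no intervention, or do not stop or delay treatment. For such changes these summaries, with the listings, are the main record.

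The liver table has a further ambiguity: it describes post-baseline elevations but includes Screening as a time point, and it defines no baseline. Protocol 7.3.3 excludes ALT or AST only from 5 times the upper limit of normal, so a patient can enter already above the table's threshold of 3 times.

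**Working it through.** The plan gives no figure on this point to reproduce. The check sets the passages side by side, then does the day arithmetic and an illustration.

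**1. Which reference is available and which is shown**

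| Parameter | Visits sampled | At First Dose row in SAP? | Last value before Period 1 dose | Last scheduled value before Period 2 dose |
|---|---|---|---|---|
| Urinalysis | 1, 3, 6, 9 | Yes | Visit 3 | Visit 6 |
| Vital signs | 1, 3, 6, 9 | Yes | Visit 3 | Visit 6 |
| Chemistry, hematology | 1, 6, 9 | No | Screening (Visit 1) | Visit 6 |
| ALT, AST, bilirubin elevations | 1, 6, 9 | No | Screening (Visit 1) | Visit 6 |

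The absence of a Visit 3 draw explains the use of Screening in Period 1. It does not explain the omission of Visit 6 in Period 2.

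**2. Age of the reference at Visit 9** (nominal study days)

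- From Screening: Day -21 to Day 38 = 38 + 21 = 59 days. Over the Visit 9 window of ±7 days this is 52 to 66. A later Screening date shortens it.
- From Visit 6: Day 17 to Day 38 = 38 − 17 = 21 days.

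**3. Share of the table concerned**

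Allocation is 1:1 with at least 15 completers per sequence (SAP 2.2). With 30 completers, 15 of the 30 values in each treatment column come from Period 2. Only those with an abnormality that arose in Period 1 and persisted to Visit 9 are affected.

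**4. Illustration of the dilution**

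Assumptions, none of which is in the documents: a proportion p of patients develops an abnormality on MS1819, the same in both periods; a fraction f of those arising in Period 1 is still abnormal at Visit 9; PERT causes none; all 30 complete.

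- MS1819 column: 30p patients normal at Screening and abnormal at 3 weeks.
- PERT column, Screening as reference: 15 × p × f, all from MS1819-PERT.
- Displayed difference: (30p − 15pf)/30 = p(1 − f/2).
- PERT column, counting only abnormalities absent at Visit 6: 0, so the difference stays at p.

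| p | f = 0 | f = 0.5 | f = 1 | Visit 6 as reference |
|---|---|---|---|---|
| 5% | 5 points | 3.75 | 2.5 | 5 |
| 10% | 10 points | 7.5 | 5 | 10 |
| 20% | 20 points | 15 | 10 | 20 |

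For p = 10%, the MS1819 column holds 3.0 of 30 expected patients. The PERT column holds 0, 0.75 or 1.5 as f goes from 0 to 0.5 to 1.

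**5. The two sequences are not alike**

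Patients stay on prestudy PERT during screening (Protocol 8.1). In PERT-MS1819, Screening and Visit 6 are therefore both values on PERT, after at least a month on a stable dose, and differ only by whatever happens to arise in between. In MS1819-PERT, Visit 6 is the first laboratory value on MS1819. The material effect is there.

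**The case against.** The strongest case for the SAP runs as follows. With no Visit 3 sample, Screening is the only pre-treatment value common to both sequences. The main table shows values rather than changes. Visit 6 is not dropped: it is the 3-week value of the first treatment, so the columns already compare each patient at the end of both treatments. Protocol 9.7 defines new transaminase elevations as those arising since screening. Visit 6 is itself an on-treatment value, so recovery from an MS1819 effect would look like improvement on PERT, and an elevation on PERT that worsens on MS1819 would not count as new. All results are listed, adverse events are assigned to a period by onset or worsening, and the safety analysis is descriptive.

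Much of this stands, and it rules out several stronger readings that a reader might draw:

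- That Period 1 abnormalities are moved to the wrong treatment. They are not. They appear under the treatment on which they arose and, if they persist, again under the other.
- That an MS1819 signal could be hidden. It stays in the MS1819 column; only the contrast with PERT shrinks.
- That every Period 2 value is distorted. Only abnormalities persisting to Visit 9 are duplicated.
- That the shift tables use Screening. The text does not say so, and the table specifications are a separate document not available here.
- That Visit 6 should replace Screening. Given the lack of washout and Protocol 9.7, that would be debatable.

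What the objection does not answer is why Period 2 should lack a reference that SAP 3 already defines and the schedule already supplies. Protocol 9.7 guides monitoring of individual patients; it does not settle how a table by treatment should show where an abnormality began.

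**Conclusion.** The point holds in limited form. SAP 8.5 does not carry through the SAP 3 convention for chemistry, hematology and liver elevations, and leaves the shift-table baseline unstated. The consequence is double display of abnormalities that arise in Period 1 and persist to Visit 9, mainly MS1819 abnormalities shown again under PERT in the MS1819-PERT sequence. That can dilute the displayed difference by a factor of 1 − f/2, at most one half under the assumptions above (10 to 5 points at an assumed 10% incidence and full persistence) and not at all if nothing persists. Incidence and persistence are not in the documents, so no actual size can be given. No test or decision rule depends on these tables, and the data remain in the listings. The change is still worth making before the tables are programmed, because safety is a primary objective and the samples are already scheduled.

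**What to change.** In SAP 8.5:

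1. Add an At First Dose row for chemistry and hematology, defined as the last value before the first dose of that treatment: Screening for Period 1, Visit 6 for Period 2.
2. State the baseline for the shift tables on the same basis.
3. In the ALT, AST and bilirubin table, show Period 2 elevations already present at Visit 6 separately from those first seen after crossover, and say what baseline the term post-baseline refers to.
4. Keep the Screening-referenced display alongside, because Visit 6 is an on-treatment value and Protocol 9.7 follows elevations since screening.

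The cost is SAP wording and a little extra programming. No new samples or visits are needed. The drawback is that the first-dose reference differs in kind between periods: always on prestudy PERT in Period 1, but on the first study treatment in Period 2. A footnote should say so.

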- Collect blood samples for vitamin determination (A, D, E, and K)
- Collect a serum sample for circulating anti-LIP2 lipase antibodies and MS1819-SD concentrations
- Record all fat, protein, and dose of study drug taken with every meal and snack during the confinement period

At the end of the supervised confinement (once the second blue dye marker sample has been collected), patients will crossover to their new treatment). Patients randomized to MS1819-SD will begin treatment on their prestudy porcine PERT. Patients randomized to their prestudy porcine PERT will begin treatment on MS1819-SD.

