## **9.7 Hepatic Monitoring**

The following guidelines are provided for the management of serum transaminase elevations in patients with new, clinically-meaningful increases in liver function tests occurring during the study. All cases of new (ie, since screening) elevations in ALT or AST  $\geq 3$  times ULN or any questions concerning the management of a patient with elevated serum transaminases should be discussed with the study Medical Monitor.

---

Patients who experience a new (ie, since screening) elevation in ALT or AST level to  $\geq 3 \times$  ULN OR total bilirubin  $\geq 1.5 \times$  ULN will have hepatic monitoring until one of the following occurs:

- Withdrawal from study if elevation in ALT or AST level to  $\geq 3 \times$  ULN is associated with a rise in total serum bilirubin to  $\geq 2 \times$  ULN (without laboratory findings of cholestasis [elevated serum alkaline phosphatase  $\geq 2 \times$  ULN])
- Withdrawal from study if elevation in ALT or AST level to  $\geq 5 \times$  ULN is associated with new or exacerbated gastrointestinal (GI) symptoms (ie, nausea, vomiting, right upper quadrant pain, and/or jaundice) and other causes are not evident
- Withdrawal from the study if elevation in ALT or AST is  $\geq 10 \times$  ULN regardless of serum bilirubin level

Causes of acute elevation of transaminases should be considered and ruled out (e.g., viral hepatitis, concomitant medications).

Patients discontinued from study drug administration should resume porcine PERT therapy according to physician prescription.

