9.2.2.5 Serum Liposoluble Vitamin (A, D, E, and K) Levels

Analyses of certain lab values will be undertaken to evaluate markers of nutritional status. Specifically, the laboratory parameters to be summarized will include blood levels of vitamin A, D, E, and K. Vitamin A, D, E, and K levels will be evaluated at Visits 1, 3, 6, 9, and 10.

Vitamin A, D, E, and K levels will be summarized by treatment group for Visit 3 (At Randomization), At First Dose, and at 3 Weeks Post First Dose, as described in Section 3, using descriptive statistics.

Vitamin A, D, E, and K levels will be listed for all subjects in the mITT population.

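### In SAP 8.5, a liver elevation that arises on the first treatment and persists to Visit 9 appears under both treatments, and the elevation table does not show that it predated the second

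*SAP*

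**What the plan says.** SAP 8.5 sets two time points for the descriptive laboratory tables: "Values at Screening and at 3 weeks post first dose, as described in Section 3, for laboratory parameters for hematology and clinical chemistry". The elevation table (ALT and AST at 3 x ULN or more, bilirubin at 1.5 x ULN or more) uses the same two: "total bilirubin (≥ 1.5 times ULN) will be summarized by treatment group at Screening and at 3 Weeks Post First Dose". The elevations are called post-baseline, but no baseline is defined. Shift tables are also planned by treatment group, without a stated starting visit. Individual results are listed.

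SAP 3 puts safety laboratory data on a clock that restarts with each treatment: "the measurement at first dose will be Visit 3 if a subject is randomized to the MS1819-PERT sequence, and Visit 6" for the opposite sequence. The other parameter groups named there use that first-dose measurement. For vital signs: "Values at Visit 3 (At Randomization), At First Dose, and at 3 Weeks Post First Dose, as described in Section 3, in systolic". For vitamins: "Vitamin A, D, E, and K levels will be summarized by treatment group for Visit 3 (At Randomization), At First Dose". Urinalysis, malabsorption symptoms, weight and BMI are handled the same way.

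The protocol draws chemistry at Visit 6 (8.2.3: "Collect samples for hematology, clinical chemistry, PT/INR, and aPTT"), and the switch comes later in that visit: "At the end of the supervised confinement (once the second blue dye marker sample has been collected), patients will crossover to their new treatment". There is no washout (protocol 7.1, SAP 2.2). Hepatic monitoring in protocol 9.7 uses a different reference: "All cases of new (ie, since screening) elevations in ALT or AST".

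**The concern.** SAP 8.1 tabulates safety by the treatment actually taken, whatever the period, so that each patient's tolerability of MS1819-SD can be compared with the same patient's tolerability of PERT. For a treatment given second, the relevant starting value is the one at the end of the first treatment. That value is collected, but in the descriptive and elevation tables it appears only as the first treatment's outcome. An abnormality carried over the crossover then adds a case to the second treatment's column.

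Safety is a primary objective. Under protocol 9.1.1, a laboratory abnormality without symptoms that needs no intervention and does not stop or delay study medication is not an adverse event. For such findings SAP 8.5 is the main planned summary, and the adverse event tables would not fill the gap.

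**Working it through.** The plan gives no figure to reproduce here, so the check traces the counting rule.

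**Inputs.**
- Chemistry and hematology are drawn at Screening, Visit 6 and Visit 9, and not at Visit 3 (protocol 7.1.1 Table 1, 8.1.1, 8.2.1, 8.2.3, 8.3.2).
- The clock restarts with each treatment (SAP 3).
- Columns follow actual treatment regardless of period (SAP 8.1).
- Withdrawal triggers are in protocol 9.7.

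**Step 1: map the time points.** Given these draws, three weeks after first dose can only be Visit 6 for the first treatment and Visit 9 for the second.

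**Step 2: trace one patient.** Take an illustrative ALT of 1, 4 and 4 x ULN at Screening, Visit 6 and Visit 9. Counts are MS1819-SD / PERT.

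| Counting rule | MS1819-SD first | PERT first |
|---|---|---|
| Status at each time point (SAP 8.5 text) | 1 / 1 | 1 / 1 |
| New since Screening | 1 / 1 | 1 / 1 |
| New since the start of that treatment (Screening, then Visit 6) | 1 / 0 | 0 / 1 |

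Two or three such patients in the MS1819-SD-first sequence give 2/2 or 3/3 under the SAP text, against 2/0 or 3/0 with the Visit 6 reference. Reading post-baseline as new since Screening, the sense used in protocol 9.7, does not change the double appearance. The Screening entry is normal and gives no hint of it.

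**Step 3: can such a patient reach Visit 9?** Protocol 9.7 withdraws patients in three situations:
- ALT or AST at 3 x ULN or more with bilirubin at 2 x ULN or more and no cholestasis;
- ALT or AST at 5 x ULN or more with new or worse GI symptoms and no other evident cause;
- ALT or AST at 10 x ULN or more.

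An isolated elevation from 3 to below 10 x ULN that meets none of these can continue into the second period.

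**Step 4: size, under assumptions only.** Let p1 and p2 be the risks that an elevation arises during a period on MS1819-SD and on PERT, and q the share of first-period elevations still present at Visit 9. None of these is in the documents. Assume equal sequences, independence and the same q for both treatments.
- MS1819-SD column: 0.5 x [p1 + 1 - (1 - p1)(1 - p2 q)]
- PERT column: 0.5 x [p2 + 1 - (1 - p2)(1 - p1 q)]
- Difference: (p1 - p2)(1 - q/2)

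Relative to a contrast in onset by treatment, the table keeps 100%, 87.5%, 75% or 50% at q = 0, 0.25, 0.5 or 1. With assumed risks of 10% and 2% (8.0 points), it would show 10.45% v 4.45% (6.0 points) at q = 0.5 and 10.9% v 6.9% (4.0 points) at q = 1. This shows the direction and the outer limits. It is not an estimate for this trial.

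**The case against.** **Counting under both treatments is a legitimate convention.** The table reports whether a value was elevated at the end of each treatment. SAP 8.3 likewise attributes an adverse event that occurs in both periods to both. This stands: a reader might infer that the counts are wrong, and they are not. What is missing is the information needed to attribute them.

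**A Visit 6 reference may already exist elsewhere.** A shift table needs a starting value, and under SAP 3 Visit 6 is a natural one for the second treatment. The Table Display Specifications are an attachment that is not available here. A reader might infer that SAP 8.5 shows the pre-crossover value nowhere. The text supports that only for the descriptive and elevation tables. A Visit 6 start in the shift tables would not change the elevation counts.

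**The missing first-dose column follows from the schedule.** The other groups are measured at Visit 3, and chemistry and hematology are not. This stands as a reason to use Screening for the first treatment, so the contrast with vital signs and vitamins is weak evidence of an oversight. It does not explain leaving the Visit 6 value out for the second treatment.

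**The size is assumed.** This stands. A reader might infer that the table understates an MS1819-SD liver effect by a known fraction. Neither the risks nor the persistence is in the documents, patients enter on at least one month of stable PERT, and the withdrawal rules remove the largest or symptomatic elevations.

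**The consequences are small.** This stands too. With about 38 patients and three scheduled draws each, cases can be traced in the listings. New ALT or AST elevations of 3 x ULN or more go to the Medical Monitor, and the DSMB reviews the full data at the end.

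**Conclusion.** The point holds as a minor weakness of attribution. In the descriptive chemistry and hematology summaries and in the elevation table, an abnormality that begins on the first treatment and lasts to Visit 9 appears under both treatments, and neither display shows that it came before the second. This follows from the SAP text and the draw schedule, whichever way post-baseline is read. It blurs the within-patient comparison and does not invalidate any count.

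The effect per patient is exact: one extra case in the second treatment's column. The number of such patients is unknown, and the 50% to 100% range in the working rests wholly on its assumptions. No decision rule uses the table. The conclusion does not extend to the shift tables, whose starting visit is unstated.

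**What to change.** - Keep the planned counts in SAP 8.5. In the elevation table, split second-treatment elevations into those already present at Visit 6 and those new or worsened since Visit 6.
- For the chemistry and hematology shift tables, name Screening as the starting visit for the first treatment and Visit 6 for the second, unless the Table Display Specifications already do so.
- Add a footnote that the Visit 6 draw may precede the crossover by up to the 7-day confinement, so onset in that gap has to be traced from the listings. It should also say that an elevation already present at Visit 6 may still have a contribution from the second treatment.
- Leave Screening as the reference for monitoring in protocol 9.7.

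The cost is one or two SAP sentences, one extra set of rows in one table and a mixed reference that the footnote must explain. The data are already collected, no count is removed, and no protocol change is needed.

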- I On the basis of laboratory safety values, unscheduled hepatic monitoring testing may be performed in Patients with new, clinically-meaningful increases in liver function tests occurring during the study, in consultation with study designated Medical Monitor. These tests are to be done through the central labs.
- J Fecal pancreatic elastase will be sent and analysed by the central laboratory.
- K At the end of V9, Patients should resume their prescribed porcine PERT. For Patients that were on their prescribed porcine PERT during V9 no change will be needed.

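### The liver elevation table counts only Screening and the scheduled 3-week value, one analyte at a time, so later peaks are not counted and protocol 9.7 conditions cannot be read from it

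*SAP*

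**What the plan says.** SAP section 8.5 plans a summary of "Post-baseline elevations in alanine aminotransferase", AST and total bilirubin. The thresholds are 3 times ULN for each transaminase and 1.5 times ULN for bilirubin, and the results "will be summarized by treatment group at Screening and at 3 Weeks Post First Dose". For laboratory data in general, SAP section 3 states: "These endpoints will be summarized relative to the time of first dose on a given study treatment". It gives no rule for unscheduled values.

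Two other outputs in SAP section 8.5 bear on the point. One covers the critical tests: "Shift tables based on classification of values with respect to the reference range will be summarized for the safety population". The other is a listing: "Hematology, clinical chemistry, hepatic monitoring, urinalysis, and pregnancy results will be presented in data listings for subjects in the safety population".

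On the protocol side, a footnote to Table 1 says that "unscheduled hepatic monitoring testing may be performed in Patients with new, clinically-meaningful increases in liver function tests occurring during the study", through the central laboratory. Under section 9.7, a patient with a new ALT or AST of at least 3 times ULN, or bilirubin of at least 1.5 times ULN, "will have hepatic monitoring until one of the following occurs". Three withdrawal conditions follow. The first is a joint one, in which the transaminase rise "is associated with a rise in total serum bilirubin to" at least 2 times ULN, without cholestasis. The second is a transaminase of at least 5 times ULN with gastrointestinal symptoms and no other evident cause. The third is a transaminase of at least 10 times ULN whatever the bilirubin.

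**The concern.** Safety is a primary objective, and protocol section 10.1 calls establishing the safety of the dose the main goal of the study. The protocol's own liver conditions depend on how high a value goes and on whether transaminase and bilirubin rise together. The table is built on neither. It takes one scheduled on-treatment value per treatment and treats each analyte alone. A reader of the by-treatment table could see fewer or milder elevations than the trial recorded, and could not tell from it whether any patient met a section 9.7 condition.

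The sentence also contradicts itself, because an elevation at Screening is not a post-baseline elevation.

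**Working it through.** The plan gives no figure for this table, so the check sets the passages side by side.

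**Which values can enter the table.** In the schedule of assessments, chemistry is marked at Visits 1, 6 and 9 only. Visit 1 is Screening. Visits 6 and 9 end the two treatment periods, so each is the 3-week value for one treatment. That gives one scheduled on-treatment value per treatment and patient. The SAP defines no maximum-value or any-time row.

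**When monitoring tests fall.** Protocol sections 8.2.3 and 8.3 make the crossover immediate once the Visit 6 stool collection is complete, with no washout. Tests prompted by a Visit 6 result therefore tend to fall between Visits 6 and 9, on the other treatment. Tests prompted by a Visit 9 result fall after all patients have gone back to PERT, and Visit 10 has no scheduled chemistry. In neither case does a 3-week column receive the value.

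**What the table shows in each situation.**

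| Course of the liver tests | Table as planned | Not shown |
|---|---|---|
| ALT at least 3 times ULN at Visit 6 or 9, no further rise | Counted | Nothing |
| ALT from 3 to below 5 times ULN at Visit 6 or 9, then at least 5 or 10 times ULN on monitoring | Counted once, at 3 times ULN | The higher multiple |
| ALT at least 3 times ULN at Visit 6 or 9, bilirubin at least 2 times ULN later | ALT row only | The bilirubin rise and the joint event |
| Both analytes over threshold at the same visit in one patient | One count in each row | That both belong to the same patient |
| Elevation first found at an unscheduled test and absent from, or not measured at, the scheduled visit | No count | The whole event |

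The first row shows that the table works where the scheduled value tells the whole story. The last row is likely to be the least common, since the Table 1 footnote ties unscheduled testing to increases already seen.

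**Whether other outputs fill the gap.**
- Listings carry the values but give no count by treatment.
- Shift tables classify by reference range, not by multiples of ULN. Their time points are not stated, and the list of critical tests is in an attachment that is not available here.
- Protocol section 9.1.1 leaves certain laboratory abnormalities without clinical manifestations out of the AE definition, so AE tables are not a sure substitute.
- SAP section 8.3 assigns AEs to a period by date. No such rule exists for unscheduled laboratory values.

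**Illustration of what one uncounted patient would mean.** Protocol section 10.2 and SAP section 2.6 say that an event not seen in 30 completers has a 95% interval from 0% to 10%. The rule of three gives 3/30 = 10%, and the one-sided 95% bound is 1 − 0.05^(1/30) = 9.5%, so the figure reproduces in that form. The two-sided exact upper bound is 1 − 0.025^(1/30) = 11.6%. If one patient of 30 (1/30 = 3.3%) had the event but was not counted, the correct one-sided bound solves (1 − p)^30 + 30p(1 − p)^29 = 0.05, which gives p = 14.9%. One missed case is enough to undo the statement that the event is below 10%. This shows sensitivity only and does not predict that a case will be missed.

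**The case against.** The strongest reply is that nothing is lost. Hepatic monitoring results are listed for the safety population, and with about 38 patients each monitored case can be read individually. The table's thresholds are the same as the section 9.7 triggers, so a trigger found at Visit 6 or 9 is counted. A patient withdrawn under section 9.7 would appear in the disposition table with a reason (SAP section 5.1) and probably among TEAEs leading to discontinuation (SAP section 8.4). Shift tables are planned as well. All of this stands, and it confines the defect to one table. It does not supply a count by treatment, a ULN multiple or a joint elevation.

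A second reply is that the Screening column is useful. This also stands. Exclusion criterion 6 bars transaminases only from 5 times ULN upward and makes an exception for Gilbert's syndrome, so patients can enter with values over the table's thresholds. The column helps to separate existing elevations from new ones. Only its post-baseline label is wrong.

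A third reply is that a plain worst-value rule could charge a persisting period 1 elevation to the second treatment. That is correct, and the fix has to deal with it.

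A reader might infer that the table leaves out the liver values of everyone who withdraws early, and put the number at the planned dropouts, 38 − 30 = 8. The documents do not support this. The Early Withdrawal visit in protocol section 8.3.3 includes no chemistry, so for most of these patients there is no further value to omit. A patient who leaves after Visit 6 already has a scheduled value for the first treatment. The point applies to a withdrawn patient only where an unscheduled test was done.

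**Conclusion.** The point holds for the by-treatment elevation table. As written, the rule can under-count the extent of liver elevations, and it cannot show whether the joint or higher-multiple conditions of protocol section 9.7 were met. This is a stated rule with that effect, not a detail left open. Its size in patients cannot be derived, because the documents give no expected rate of elevations or of unscheduled tests.

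The conclusion rests on two readings: that the 3-week time point means the scheduled Visit 6 or 9 value, and that the unavailable table specifications do not already add a worst-value row. A reader might go further and say that the safety report would hide a patient who met a withdrawal condition. That is not supported, because listings and disposition would still show the patient. The change is worth making because safety is a primary objective and the added rows need no new data collection.

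**What to change.** In SAP section 8.5:

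1. Add, by treatment, the number of patients with any elevation after first dose, taking the worst ALT, AST and total bilirubin from scheduled and unscheduled tests.
2. Give rows for the ULN multiples already in protocol section 9.7, and a row for transaminase and bilirubin elevations occurring together in the same patient.
3. Keep Screening as a separate column labelled baseline, and apply the post-baseline label only to later values.
4. State the attribution rule. Assign each elevation to the treatment being taken at its onset. Count a value drawn after crossover against the second treatment only if it is new or has worsened from the end of period 1. Show follow-up values, drawn after the second treatment ends, separately.

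The cost is one paragraph and one table. Some judgment on attribution after crossover remains and should be exercised before database lock.

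A separate matter for the sponsor is that protocol section 7.3.4 encourages withdrawn patients to attend for follow-up safety investigations, while the visit described in section 8.3.3 lists no chemistry. The two passages should be reconciled. That is a question of data collection, which wording in SAP section 8.5 cannot settle.
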